6.4 RECEIPT AND ADMINISTRATION OF ELAD CARTRIDGES

Upon receipt and inspection of the ELAD cartridges by the VTL ELAD Specialist, the system will be taken to the bedside and treatment will be started as soon as possible. In all cases, treatment should be initiated according to [Section 5.4](#).

6.5 ELAD CARTRIDGE REPLACEMENT

ELAD cartridges may need to be replaced during treatment due to ELAD cartridge performance or interruption of treatment greater than 6 continuous hours.

If scheduled End of Study Day procedures occur while the subject is awaiting new cartridges, those scheduled procedures will be carried out in accordance with the protocol. The 24-hour safety evaluations and UF culture and samples performed on treatment day 1 must be repeated if the ELAD cartridges are replaced during treatment (see [Section 5.5.2](#), [Section 5.6.2](#), and [Section 5.6.4](#)). In addition, if ELAD treatment is stopped for more than 6 hours, the Pre-ELAD safety assessments (See [Section 5.4.2.1.1](#)) in accord with the pertinent Exclusion Criteria [2](#), [3](#), [4](#), [7](#), [9](#), [10](#), [15](#), and [16](#) relative to the safety evaluation time point will be performed. Administration of 100 mg hydrocortisone and 50 mg diphenhydramine do not need to be repeated prior to initiation of ELAD treatment after cartridge replacement.

6.6 INTERRUPTION OF ELAD TREATMENT

ELAD treatment may be interrupted. If the interruption is for a period of *less* than 6 hours then ELAD may be restarted with the same set of cartridges. If ELAD treatment is interrupted for a period of *more* than 6 hours but less than 72 hours (e.g. to allow for the conduct of a diagnostic or therapeutic procedure or for management of an adverse event, or should there be a need to interrupt the use of anticoagulants), then a new set of ELAD cartridges must be used if treatment of the subject will continue. In order for ELAD treatment to be restarted with a second set of cartridges after more than 6 hours, the subject must meet the same safety eligibility criteria as are required prior to the initiation of the first set of cartridges (See [Section 5.4.2.1.1](#) and [Section 6.5](#)). If there is a need to replace ELAD cartridges, the subject's overall ELAD treatment duration will be calculated based from the initial start of treatment. If the subject's ELAD treatment is interrupted for greater than 24 hours, the treatment period may be extended, not to exceed a total of 120 treatment hours. The maximum period between stopping treatment and starting with a new set of cartridges is 72 hours.

6.7 CRITERIA FOR DISCONTINUATION OF ELAD TREATMENT

ELAD treatment will be discontinued and will not be restarted if any of the discontinuation criteria listed in [Section 3](#) are met.

6.8 ELAD SYSTEM ACCOUNTABILITY

6.8.1 Shipment of ELAD Cartridges

The ELAD cartridges will be packed in a temperature controlled, secured shipping container to maintain temperature within specifications outlined in the [ELAD System Operator's Manual](#). The shipment will be sent to the Investigator or designee by rapid courier. Final ELAD cartridge accountability records will be maintained as described in [Section 6.8.4](#).

6.8.2 ELAD Cartridge Inspection and Storage

The ELAD cartridges may be received at the study site by the ELAD Specialist or designee. ONLY the ELAD Specialist will open, inspect, and store the ELAD cartridges as per the ELAD System Operator's Manual. ELAD cartridge accountability will be documented as described in [Section 6.8.4](#).

ELAD cartridges may remain stored in a temperature controlled environment for up to 60 hours according to the "Begin Use By" date and time indicated on the label. Cartridges that have been stored longer than 60 hours before they are used in ELAD treatment will be returned to VTL or designee or destroyed by the ELAD Specialist according to the institution's policies.

6.8.3 Packaging and Labeling of Cartridges

The ELAD cartridges will be labeled with the protocol number, ELAD cartridge identification, conditions for storage, subject number, Investigator's name and telephone number, "Begin Use By" date and time (60 hours allotted for transport and storage until installation into ELAD System), and "Complete Use By" (date and time after which the cartridges can no longer be used for subject treatment). Other labels must not be adhered to the cartridges to obscure any of this labeling information. The final label will be adapted to the requirements of the individual country where the study is being performed in accordance with local regulations.

6.8.4 Dispensing and Accountability of Cartridges

ELAD cartridges will be dispensed to the study site for subject use. Other labels must not obscure the VTL label, especially the cautionary statement on Investigational Use, which is required verbatim by law.

The ELAD Specialist will maintain complete accountability records of all ELAD cartridges shipped to the study site. The accountability records are provided to the study site upon completion of treatment. The ELAD cartridge accountability log will include the following:

- Subject Identification Number
- ELAD cartridge reception, inspection, and storage
- ELAD cartridge final disposition
- ELAD cartridge lot number

The ELAD Specialist will also provide the study site with copies of the shipping records of the ELAD cartridges and a copy of the Certificate of Analysis as part of the subject's source documentation.

The ELAD cartridges are to be prescribed only by the Investigator named on the Form FDA 1572 (or equivalent) and listed on the Delegation of Authority Log. Under no circumstances will the Investigator allow the ELAD cartridges to be used other than as directed by this protocol.

6.8.5 ELAD System Disposition

Maintenance and accountability of the ELAD System, non-mechanical materials (disposables) and supply cart will be maintained by the ELAD Specialists in accord with the [ELAD System Operator's Manual](#).

All System-related malfunctions will be noted by the ELAD Specialist and reported to VTL according to internal VTL processes.

ELAD cartridges, ELAD System, and supply cart disposition is recorded on the ELAD System Monitoring Forms. This is completed by the ELAD Specialist on site at the end of subject treatment. These forms serve as verification of the accountability (including disposition) of the ELAD System, cartridges, and supplies, and this information is available to the site personnel in the EDC system.

Each ELAD System and supply cart has a unique identification number that will be used for this purpose and will include date of arrival as well as date shipped out of the investigational site.

Any issues involved with the identity, quality, durability, reliability, safety, or performance of the system or any of its components will be recorded on the ELAD System Monitoring Forms by the ELAD Specialists. Any investigational product-related subject adverse events will be reported as detailed in [Section 9](#).

6.8.6 Cleaning of Equipment after Discontinuation of ELAD Treatment

At the conclusion of the subject's treatment and the removal of all non-mechanical (disposable) materials from the ELAD System, the ELAD Specialists will clean all surfaces of the ELAD System using the appropriate disinfectant solution(s) according to the ELAD Bedside Unit disinfection procedure. The cleaning of the equipment designated for ELAD treatment will be noted on the ELAD Declaration of Decontamination Status Form.

7 STATISTICS AND METHODS OF DATA ANALYSIS

7.1 SAMPLE SIZE RATIONALE

The sample size is based on experience from the VTI-208 study.

Analysis of the VTI-208 data suggests that in a group of subjects meeting the inclusion criteria for VTL-308 it might be reasonably anticipated that the hazard rate in the control group will be 0.004 and the hazard ratio 0.4 in favor of the ELAD group. Under the assumption of a proportional hazards model, this leads to median survival estimates of approximately 175 days and 438 days for Control and ELAD subjects, respectively.

The VTL-308 inclusion criteria have been established to reflect the same study population as that enrolled in a subset of the VTI-208 population with baseline criteria including MELD <30, age <50, INR \leq 2.5, creatinine <1.3 and serum total bilirubin \geq 16mg/dL, to define the ITT population, with key safety criteria also applied prior to initiation of ELAD treatment and at End of Study Day 2 (EOSD 2) in the Control group to establish the mITT population. Applying these criteria to the analysis of the primary endpoint of overall survival in the ITT population, and assuming: 1) that this prospectively-defined population behaves similarly to this subgroup of the VTI-208 study; 2) the use of a log-rank test comparing two survival curves with a two-sided significance level of 0.05; 3) exponential survival curves with proportional hazards; 4) uniform accrual with an accrual time of at least 720 days and a minimum follow-up time of 90 days; and 5) a drop-out rate of 10%, a sample size for VTL-308 of 75 subjects per group with 1:1 allocation is consistent with power of at least 0.95 with estimated median survival times of 175 and 438 days respectively.

Due to the distribution of subjects between the ITT and mITT group it may be necessary to enroll more than 150 subjects total in order to ensure that there are a minimum of 75 subjects actually treated with ELAD in the ITT population. Consequently, enrollment may continue until ELAD treatment has been initiated on 75 subjects.

The proportional hazards model modified in accord with findings from Study VTI-208 estimates that approximately 55 deaths are anticipated as the total number of events required to achieve approximately 95% power under these assumptions. If the total number of observed events in the ITT primary population is less than this number after all 150 enrolled subjects complete Study Day 91, are lost to follow up, withdraw consent, or die before that Study Day, then the study may continue until a minimum of 55 deaths are recorded. This provision is intended to ensure that the desired power is achieved in the ITT population even if the event rate is lower than would be anticipated from the reference study, VTI-208.

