1.3 SAMPLE SIZE RATIONALE

The sample size is based on experience from the VTI-208 study.

The VTL-308 inclusion criteria have been established to reflect a subset of the VTI-208 population, i.e. the VTI-208 population with baseline criteria of MELD <30, age <50, INR \leq 2.5, creatinine <1.3 mg/dL and serum total bilirubin \geq 16 mg/dL.

The key design feature of the VTL-308 Protocol is that the primary analysis of treatment effect on overall survival is based on a log-rank statistic having two-sided significance level of 0.05. This primary analysis will be performed when the last of 150 randomized subjects has been followed for at least 91 days. Sample size adjustments may be made only in the instance in which more than 150 randomized subjects would be needed in order to achieve the minimum threshold of 55 deaths at the time of that analysis.

When the study is nearing completion of enrollment, the total number of deaths occurring through that time will be calculated, along with the mortality rate, based on the enrollment rate per month and the time to death. Based on these calculations a projection will be made of the total number of subjects that will need to be enrolled to achieve the minimum threshold of 55 deaths at the time of study data lock (estimated to be approximately 5 months after last patient enrolled). The total sample size may then be adjusted accordingly.

Analysis of the VTI-208 data suggests that in a group of subjects meeting the inclusion criteria for VTL-308, it might be reasonably anticipated that one-year survival will be in the range from 40% to 48% in the Control group. Under the assumption of a proportional hazards model, if the hazard ratio is 0.4 in favor of the ELAD group, this leads to the anticipation that one-year survival will be in the range from 69.5% to 74.5% in the ELAD subjects.

The rationale for the sample size is based on the following assumptions:

- the analysis of the primary endpoint of overall survival will be conducted in the ITT population;
- the prospectively defined population behaves similarly to the corresponding subgroup of the VTI-208 study;
- the log-rank test will be used to compare two survival curves using a two-sided significance level of 0.05;
- one-year survival will be in the range from 40% to 48% in the Control group and in the range from 69.5% to 74.5% in the ELAD group;
- the accrual distribution will be uniform with an accrual time that will be at least 720 days;

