- the rate of missing data will be in the range from 0% to 10%; and
- the primary analysis will be the time when at least 55 deaths have occurred and the time when the last enrolled subject has been followed for at least 91 days. It follows that a sample size for the VTL-308 trial of 75 subjects per group with 1:1 allocation would provide a number of events (i.e., deaths) in the range from 55 to 65, even if we assume average follow-up of only 1 year. With 55 events, the trial will have 90% power if the true hazard ratio is 0.417; with 65 events, the trial will have 90% power if the true hazard ratio is 0.447.

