5 DATABASES

Data will be collected in the Electronic Data Capture (EDC) system and other databases for the statistical analyses presented in this plan. The following table lists these databases and provides a description of the type of data being captured in each:

| Data Source | Primary Utility |
|-------------------------------|--|
| VTL-308 clinical database | Primary database for establishment of outcomes. Primary source of screening information, baseline characteristics, laboratory values, concomitant medications, adverse events (AEs), PEth lab results, ELAD Specialist data, and Home Health Care visit data. |
| VTL-308E interim data | Extension data documenting survival (at 6, 9, 12, and 24 months), transplant, incidence of cancer, and quality of life. Survival data earlier than 6 months may also be available for subjects who do not complete their Day 91 visit. Note: a snapshot of the VTL-308E database will be conducted at the time of the VTL-308 database lock to provide the updated information for the analysis of the primary endpoint of overall survival. |
| ELAD System performance files | Information recorded automatically by the ELAD System (Sorin S3/S5) documenting multiple system performance parameters during subject treatment. These data are stored in CSV format (one file per subject/cartridge set). |
| Manufacturing data | Files documenting ELAD cartridge performance and product release parameters such as albumin, transferrin, glucose consumption, and oxygen utilization, along with date of manufacture, and date of shipping. |

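### The 55-death floor gives about 92.5% power at a hazard ratio of 0.4, not the 95% stated in Protocol 7.1, and the SAP does not fix when those deaths are counted

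*Protocol*

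**What the plan says.** Protocol 7.1 bases the sample size on a two-sided 0.05 log-rank test, 1:1 allocation and exponential survival, and anticipates that "the hazard rate in the control group will be 0.004 and the hazard ratio 0.4 in favor of the ELAD group". It then states that "approximately 55 deaths are anticipated as the total number of events required to achieve approximately 95% power under these assumptions". If fewer than 55 deaths have been seen when all 150 subjects have finished Day 91 or left the study, follow-up may go on until 55 are recorded. Of this rule the protocol says: "This provision is intended to ensure that the desired power is achieved in the ITT population even if the event rate is lower".

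SAP 1.3 keeps the floor of 55 but not the 95% statement. It says that 75 per group "would provide a number of events (i.e., deaths) in the range from 55 to 65" and that "With 55 events, the trial will have 90% power if the true hazard ratio is 0.417"; for 65 events the corresponding hazard ratio is 0.447.

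On timing, the SAP has these statements:

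- **Section 1.3, first statement.** The primary analysis takes place when the last of 150 subjects has at least 91 days of follow-up, and the 55 deaths are wanted at that analysis.
- **Section 1.3, enrolment projection.** The sample size may be raised to "achieve the minimum threshold of 55 deaths at the time of study data lock (estimated to be approximately 5 months after last patient enrolled").
- **Section 1.3, last assumption.** "the primary analysis will be the time when at least 55 deaths have occurred", together with 91 days of follow-up on the last subject.
- **Section 5.** "a snapshot of the VTL-308E database will be conducted at the time of the VTL-308 database lock", to update the data for overall survival.
- **Section 7.** The primary log-rank test uses each subject's last evaluation up to Day 91 after the date of the last randomisation.

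**The concern.** The number of deaths largely fixes the power of a log-rank test. A floor on deaths is therefore only as good as the power attached to it, and the protocol offers this one as its safeguard against a low event rate. If 55 deaths do not give 95% power at the design hazard ratio, the safeguard secures less than it says.

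The timing matters for a different reason. If too few deaths have occurred, there are two ways to reach 55. Enrolling more subjects (SAP 1.3) moves the last randomisation, and the Section 7 cut-off moves with it. Following existing subjects for longer (Protocol 7.1, and a possible reading of the last assumption in SAP 1.3) does not move that cut-off. Deaths gained that way would fall outside the primary test as Section 7 is written. In an open-label pivotal trial, the data cut-off for the primary endpoint should have one reading, fixed before the data are analysed.

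**Working it through.** **Inputs.** Protocol 7.1: hazard ratio (HR) 0.4, Control hazard 0.004 per day, two-sided alpha 0.05, 1:1, 75 per group, uniform accrual over 720 days, 10% drop-out. SAP 1.3: one-year Control survival 40% to 48%, missing data 0% to 10%.

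**1. Reproduce the SAP's figures.** Schoenfeld, 1:1: the HR detectable with 90% power is exp(−2(1.960 + 1.282)/√d).

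- d = 55: 0.417
- d = 65: 0.447

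Both match SAP 1.3.

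**2. Apply the same formula to the protocol's statement.** Power = Φ(√d/2 × |ln 0.4| − 1.960), with |ln 0.4| = 0.9163.

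| Deaths | Power at HR 0.4 |
|---|---|
| 50 | 90.0% |
| 55 | 92.5% |
| 61 | 94.7% |
| 62 | 95.0% |
| 65 | 95.9% |

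Deaths needed for 95%: 4(1.960 + 1.645)²/0.9163² = 61.9, so 62. With 55 deaths, 95% power needs a true HR of exp(−2 × 3.605/√55) = 0.378.

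**3. Try other methods.**

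- HR from the stated medians (175/438 = 0.3995): 92.5% with 55 deaths.
- Freedman: 88.8% with 55 deaths; 71 needed for 95%.
- Exponential test with variance 1/d₁ + 1/d₂: 87.6% to 91.1% with 55 deaths, depending on how they split between arms.
- Simulated log-rank (20,000 trials, 75 per arm, stopped at the given death): with 55 deaths, about 91% under staggered entry and 92.5% under simultaneous entry; with 62, about 94% and 95%.
- One-sided 0.05: 96.0% with 55 deaths, but the protocol specifies a two-sided test.

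No method consistent with the stated test gives 95% with 55 deaths.

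**4. Does the floor bind?** Expected deaths per arm by time f after the last randomisation are 75 × [1 − (e^(−hf) − e^(−h(720+f)))/(720h)], with the ELAD hazard at 0.4h. The SAP hazards are −ln(0.40)/365 = 0.00251 and −ln(0.48)/365 = 0.00201 per day. The last two columns take 10% off the deaths for loss.

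| Scenario, f = 91 | Deaths | Power | Deaths × 0.9 | Power |
|---|---|---|---|---|
| Protocol, h = 0.004 | 94 | 99% | 85 | 99% |
| SAP, 40% at one year | 74 | 97.6% | 66 | 96.2% |
| SAP, 48% at one year | 64 | 95.6% | 58 | 93.6% |

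The floor does not bind in any of these.

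**5. What the cut-off could cost.** Take data lock as Day 152 after the last randomisation (an assumption for about five months). Under the protocol hazards, deaths rise from 94.4 at Day 91 to 101.7 at Day 152, so about 7 would fall after the Section 7 cut-off. If exactly 55 deaths were reached at lock, solving for h gives 0.00140 per day, which is 60% one-year Control survival. About 50 of the 55 would then fall by Day 91, and power would be 90% instead of 92.5%. With 10% loss the Control survival needed is 55%, again with about 50 deaths by Day 91.

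**The case against.** SAP 1.1 says the SAP prevails where the two documents conflict on analysis, and the SAP no longer claims 95%. The protocol's sentence is approximate in both numbers and refers to a proportional hazards model modified in the light of VTI-208, so an undescribed method cannot be excluded. The floor does not bind under any stated assumption. Sixty-two is itself a Schoenfeld figure; with staggered entry the simulated power at 62 deaths is nearer 94%. On timing, taking a database snapshot later than the analysis cut-off is normal practice. The five-month lock is a planning estimate, the SAP's explicit remedy for too few deaths is more subjects, and the 55-versus-50 illustration lies outside the assumed survival range.

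Much of this limits the weight of the point without removing it. The SAP keeps 55 as the floor and does not state its power at HR 0.4, so the protocol sentence remains the only such statement. That sentence ties its figure to the listed assumptions, and no modification is described. The snapshot in SAP Section 5 is not a conflict in itself. The conflict between SAP 1.3 (deaths projected to lock; 55 deaths as a condition of the analysis) and Section 7 (data through Day 91 only) stands.

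**Conclusion.** Both parts hold. At HR 0.4 with the stated test, 55 deaths give about 92.5% power by Schoenfeld, with simulation between about 91% and 92.5%. The type II error is therefore about 7.5%, not 5%, and 95% needs 62 deaths, seven more than stated. This does not make the trial underpowered under its own assumptions, and the separate claim that 75 per group gives at least 95% is not contradicted under the protocol hazards. The error is confined to the power claimed for the floor, and would be felt only if the event rate were low.

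The SAP also leaves the primary data cut-off open to more than one reading. The illustrated loss (90% instead of 92.5%) rests on a Day-152 lock and on Control survival of 55% to 60%, above the SAP's 40% to 48%, so it shows the mechanism and is not a forecast. Both statements should be corrected.

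**What to change.** - **Protocol 7.1.** State that 55 deaths give about 92% power at HR 0.4 and that 62 are needed for 95%, and name the formula (Schoenfeld, two-sided 0.05, 1:1). If a modified model was used, describe it.
- **SAP 1.3.** Say that the 55 deaths are those in the primary log-rank data set at its cut-off, and project enrolment to that date, not to data lock.
- **SAP Section 7.** Set the cut-off as the later of Day 91 after the last randomisation and the date of the 55th death. This matches the joint condition already in SAP 1.3.
- **SAP Section 5.** State that the VTL-308E snapshot must cover survival to that cut-off.

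The cost is wording in two documents and a stated power for the floor about 2.5 points lower. No extra patients are needed. The Section 7 change does alter the data rule for the primary endpoint and could lengthen follow-up if deaths are few, but not beyond what Protocol 7.1 and SAP 1.3 already allow.

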7.2 POPULATIONS

7.2.1 Safety

This population is defined as all subjects who are randomized and begin treatment including standard of care; analyses of this population will be based on actual treatment received. This population will include all randomized subjects assigned to the group that most accurately reflects the actual treatment that they received.

As a practical matter this means that a subject deemed an “ELAD-treatment initiation failure” that received no ELAD treatment would be assigned to the Control group. A subject that was randomized to the Control group yet received ELAD treatment would be assigned to the ELAD group.

